Enrolment in the study will be confirmed by completing the Enrolment form on the electronic case report form (eCRF). Information collected for screening failures include date of informed consent, inclusion/exclusion criteria, and serious adverse events (SAE) where relevant.

[figure not shown]
Treatment phase

Patients will start study treatment on Day 1 with everolimus 10 mg daily p.o. (either 2 x 5 mg or 1 x 10 mg tablets) in combination with exemestane 25 mg daily p.o. (25 mg tablets). Dose adjustment (reduction or interruption) will be allowed according to safety findings and dose adjustment guidelines. Study treatment will continue until disease progression, unacceptable toxicity, death, consent withdrawal or any other reason. Further treatment after progression will be at the investigator's discretion.

During the study, visits will be performed at Screening, Baseline/Treatment Day 1 (Treatment start), Week 4 (\pm 1 week), Week 10 (\pm 2 weeks), and then every 10-weekly (\pm 2 weeks) till end of treatment.

Tumor evaluations through CT scan/MRI will be performed for Screening, at Week 10, and 10 weekly thereafter. All radiological evaluations and laboratory assessments will be performed locally, at the center level. Patients will be followed up for safety for 30 days (\pm 2 days) after the last dose of everolimus. AEs/SAEs with a suspected causality to the study drug must be reported beyond this 30 days safety interval.

Figure 4-1 Study design

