7.3 Efficacy assessments

Tumor assessments are summarized in [Table 7-2](#).

Tumor response will be evaluated according to RECIST (Version 1.1) (See [Appendix 1](#)).

All patients should have at least one lesion that can be accurately measured in at least one dimension ≥ 20 mm with conventional imaging techniques or ≥ 10 mm with spiral CT as per RECIST 1.1 criteria, or in the absence of measurable disease have at least one lytic or mixed (lytic + blastic) bone lesion.

The same method of assessment and the same technique should be used to characterize each identified and reported lesion at baseline for each study tumor assessment after start of study treatment.

For patients with measurable disease at baseline, tumor progression will be evaluated at each assessment according to the RECIST 1.1 criteria (see [Appendix 1](#) for details). All patients being discontinued from the study for disease progression must have their progression documented using the RECIST 1.1 criteria.

A CT scan/MRI of the chest, abdomen and pelvis will be performed at screening and repeated at Week 10, Week 20, Week 30, Week 40, and Week 50/EOT. CT scan with contrast media should be used except for patients who are allergic/sensitive to the radiographic contrast media. Response will be assessed by local radiology review. The decision regarding patient management will remain with the local investigator. The same radiologist/physician should perform the evaluation for the entire duration of the study.

Bone scans/skeletal survey by X-ray must be performed at baseline within 6 weeks before enrolment. Positive areas on bone scans/X-ray must be assessed by MRI or CT scan with bone windows, prior to enrolment and should continue to be assessed using the same modality (MRI or CT scan) at Weeks 10, 20, 30, 40, and Week 50 or End of Treatment. Additional bone scans/X-ray should be performed if clinically indicated. Abnormalities found on subsequent bone scans/X-ray must be confirmed by MRI or CT scan.

In the absence of measurable disease at baseline, the following will be considered progression among patients with lytic or mixed (lytic + blastic) bone lesions:

- Appearance of one or more new lytic lesions in bone
- Appearance of one or more new lesions outside of bone
- Unequivocal progression of existing bone lesions.

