10.6.1.1 Overall response rate

The Overall response rate (ORR) will be provided over the study period. The ORR is the proportion of patients with a best overall response of confirmed complete (CR) or partial (PR) response at those time points. The best overall response for each patient is determined from the sequence of investigator overall lesion responses according to RECIST 1.1. To be assigned a best overall response of CR at least two determinations of CR at least 4 weeks apart before progression are required. To be assigned a best overall response of PR at least two determinations of PR or better at least 4 weeks apart before progression (and not qualifying for a CR) are required.

The ORR (best overall response of CR or PR) as well as individual response categories (CR, PR, SD, PD or unknown) measured at approximately week 20 and week 50 will be summarized using frequency tables together with their associated two-sided exact 95% confidence intervals (Clopper-Pearson method).

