Overall Response rate, overall study period	n(%)	(95% CI)	n(%)	(95% CI)	n(%)	(95% CI)
Best overall response rate ^a	xxx		xxx		xxx	
Complete Response (CR)	xx (x.x)	(xx.x, xx.x)	xx (x.x)	(xx.x, xx.x)	xx (x.x)	(xx.x, xx.x)
Partial Response (PR)	xx (x.x)	(xx.x, xx.x)	xx (x.x)	(xx.x, xx.x)	xx (x.x)	(xx.x, xx.x)
Stable Disease (SD)	xx (x.x)	(xx.x, xx.x)	xx (x.x)	(xx.x, xx.x)	xx (x.x)	(xx.x, xx.x)
Progressive Disease (PD)	xx (x.x)	(xx.x, xx.x)	xx (x.x)	(xx.x, xx.x)	xx (x.x)	(xx.x, xx.x)
Unknown (UNK)	xx (x.x)	(xx.x, xx.x)	xx (x.x)	(xx.x, xx.x)	xx (x.x)	(xx.x, xx.x)
Overall Response Rate (ORR: CR+PR) ^b	xx (x.x)	(xx.x, xx.x)	xx (x.x)	(xx.x, xx.x)	xx (x.x)	(xx.x, xx.x)
Clinical Benefit Rate (CBR: CR+PR+SD >= 24 weeks) ^c	xx (x.x)	(xx.x, xx.x)	xx (x.x)	(xx.x, xx.x)	xx (x.x)	(xx.x, xx.x)
Overall Response rate, at Week 20	n(%)	(95% CI)	n(%)	(95% CI)	n(%)	(95% CI)
Best overall response rate ^a	xxx		xxx		xxx	
Complete Response (CR)	xx (x.x)	(xx.x, xx.x)	xx (x.x)	(xx.x, xx.x)	xx (x.x)	(xx.x, xx.x)
Partial Response (PR)	xx (x.x)	(xx.x, xx.x)	xx (x.x)	(xx.x, xx.x)	xx (x.x)	(xx.x, xx.x)
Stable Disease (SD)	xx (x.x)	(xx.x, xx.x)	xx (x.x)	(xx.x, xx.x)	xx (x.x)	(xx.x, xx.x)
Progressive Disease (PD)	xx (x.x)	(xx.x, xx.x)	xx (x.x)	(xx.x, xx.x)	xx (x.x)	(xx.x, xx.x)
Unknown (UNK)	xx (x.x)	(xx.x, xx.x)	xx (x.x)	(xx.x, xx.x)	xx (x.x)	(xx.x, xx.x)
Overall Response Rate (ORR: CR+PR) ^b	xx (x.x)	(xx.x, xx.x)	xx (x.x)	(xx.x, xx.x)	xx (x.x)	(xx.x, xx.x)
Clinical Benefit Rate (CBR: CR+PR+SD >= 24 weeks) ^c	xx (x.x)	(xx.x, xx.x)	xx (x.x)	(xx.x, xx.x)	xx (x.x)	(xx.x, xx.x)
Overall Response rate, at Week 50	n(%)	(95% CI)	n(%)	(95% CI)	n(%)	(95% CI)
Best overall response rate ^a	xxx		xxx		xxx	
Complete Response (CR)	xx (x.x)	(xx.x, xx.x)	xx (x.x)	(xx.x, xx.x)	xx (x.x)	(xx.x, xx.x)
Partial Response (PR)	xx (x.x)	(xx.x, xx.x)	xx (x.x)	(xx.x, xx.x)	xx (x.x)	(xx.x, xx.x)
Stable Disease (SD)	xx (x.x)	(xx.x, xx.x)	xx (x.x)	(xx.x, xx.x)	xx (x.x)	(xx.x, xx.x)
Progressive Disease (PD)	xx (x.x)	(xx.x, xx.x)	xx (x.x)	(xx.x, xx.x)	xx (x.x)	(xx.x, xx.x)
Unknown (UNK)	xx (x.x)	(xx.x, xx.x)	xx (x.x)	(xx.x, xx.x)	xx (x.x)	(xx.x, xx.x)
Overall Response Rate (ORR: CR+PR) ^b	xx (x.x)	(xx.x, xx.x)	xx (x.x)	(xx.x, xx.x)	xx (x.x)	(xx.x, xx.x)
Clinical Benefit Rate (CBR: CR+PR+SD >= 24 weeks) ^c	xx (x.x)	(xx.x, xx.x)	xx (x.x)	(xx.x, xx.x)	xx (x.x)	(xx.x, xx.x)

Asian: Indonesia, India, Vietnam, Turkey, South Korea, Thailand, Malaysia, Taiwan or Jordan.

Non-Asian: Australia, Morocco, South Africa or Tunisia.

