^a Best overall response rate: The best response recorded from baseline assessment until progression. CR: at least two consecutive determinations of CR at least 4 weeks or one determination of CR where confirmation not required prior to PD. PR: at least two consecutive determinations of PR (or better) at least 4 weeks or one determination of PR where confirmation not required prior to PD and not classified as PR. SD: one determination of SD (any duration) prior to PD and not classified as CR or PR. PD: one determination of PD (any duration) and not classified as CR, PR or SD. Unknown: not classified as CR, PR, SD or PD.

^b Overall response rate: Patients with best overall response rate of CR or PR.

^c Clinical benefit rate: Patients with best overall response rate of CR (any duration), PR (any duration) and SD with duration of 24 weeks or longer.

N: The total number of patients in the treatment group. It is the denominator for percentage (%) calculation.

n: Number of patients who are at the corresponding category.

CI: Confidence interval. The 95% CI for the frequency distribution of each variable were computed using the Clopper-Pearson method.

Programmer note: This table is not created by Kaplan Meier method. It is a summary of descriptive statistics based on week 20 and week 50 CRF data. n is the number of patients with non-missing data.

Table 8.1.2 Overall Response Rate *Overall and in Asian Subgroup - Per Protocol Set*

This table will be created using the same layout as Table 8.1.1.

Table 8.1.3 Time to Overall Response Overall and in Asian Subgroup – Full Analysis Set

	Asian (N=xx)		Non-Asian (N=xx)		Total (N=xxx)	
	No. of patients at Risk	Event-free probability estimates (%) ^c	No. of patients at Risk	Event-free probability estimates (%) ^c	No. of patients at Risk	Event-free probability estimates (%) ^c
Time to Overall Response ^a						
Week 4	xxx	x.x	xxx	x.x	xxx	x.x
Week 10	xxx	x.x	xxx	x.x	xxx	x.x
Week 20	xxx	x.x	xxx	x.x	xxx	x.x
Week 30	xxx	x.x	xxx	x.x	xxx	x.x
Week 40	xxx	x.x	xxx	x.x	xxx	x.x
Week 50	xxx	x.x	xxx	x.x	xxx	x.x
Etc. (as appropriate)	xxx	x.x	xxx	x.x	xxx	x.x
Total number of events, n (%)	xx (xx.x)		xx (xx.x)		xx (xx.x)	
Total number of censored, n (%)	xx (xx.x)		xx (xx.x)		xx (xx.x)	
Percentiles (95%CI) (weeks) ^b						
25 th percentile	xx.x (xx.x, xx.x)		xx.x (xx.x, xx.x)		xx.x (xx.x, xx.x)	
Median	xx.x (xx.x, xx.x)		xx.x (xx.x, xx.x)		xx.x (xx.x, xx.x)	
75 th percentile	xx.x (xx.x, xx.x)		xx.x (xx.x, xx.x)		xx.x (xx.x, xx.x)	

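### SAP Table 8.1.1 requires consecutive responses where protocol 10.6.1.1 does not, its data-source note is not limited to the two visit blocks, and protocol 10.6.1.2 gives a further confirmation rule

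*SAP*

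**What the plan says.** **Protocol 10.6.1.1.** "The Overall response rate (ORR) will be provided over the study period". Best overall response is "determined from the sequence of investigator overall lesion responses according to RECIST 1.1". Only confirmed responses count. CR needs two determinations of CR, and PR needs two of PR or better, in each case at least 4 weeks apart and before progression. Nothing requires them to be adjacent. A second paragraph adds ORR and the response categories "measured at approximately week 20 and week 50 will be summarized using frequency tables".

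**Protocol Appendix 14.1.16.** The worked example for studies that require confirmation takes target-lesion sums of 200 mm at baseline, then 140, 150, 140, 160 and 160 mm. It labels the visits PR, SD, PR, PR, PR and says that the second 140 mm assessment confirms the PR.

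**Protocol 10.6.1.2.** For CBR, two determinations of CR at least 4 weeks apart are asked for in order to assign either CR or PR.

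**SAP Table 8.1.1.** The first block is headed "Overall Response rate, overall study period"; Week 20 and Week 50 blocks follow. Footnote a defines best response as "The best response recorded from baseline assessment until progression". It then asks for two consecutive determinations, or a single one where confirmation is not required. Its PR rule ends by excluding patients already classified as PR. The programmer note says of the table, exempting no block: "It is a summary of descriptive statistics based on week 20 and week 50 CRF data".

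The Table 8.1.3 footnote also says consecutive; the Table 8.2.1 footnote does not. Table 8.1.2 and subgroup Tables S1.8.1.1 to S4.8.1.1 reuse the Table 8.1.1 layout.

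**The concern.** ORR and CBR are listed as key secondary endpoints in protocol Table 3-1. The study is descriptive, so the estimate and its exact interval are the result. If the shell is stricter than the protocol about what confirms a response, some protocol responders are reported as SD. If the data source of the overall-period block is unclear, a programmer has to choose between the note and the footnote. If 10.6.1.1 and 10.6.1.2 confirm a PR differently, ORR and CBR in the same table rest on different best responses.

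**Working it through.** **1. Reproduce the protocol's example** (baseline 200 mm; PR at a fall of 30% or more from baseline; PD at a rise of at least 20% and 5 mm from the smallest sum).

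| Visit | Sum, mm | Fall from baseline | Rise from smallest sum | Status |
|---|---|---|---|---|
| 1 | 140 | 60/200 = 30% | – | PR |
| 2 | 150 | 50/200 = 25% | 10/140 = 7.1% | SD |
| 3 | 140 | 60/200 = 30% | 0 | PR, confirms |
| 4, 5 | 160 | 40/200 = 20% | 20/140 = 14.3% | not PD; carried as PR |

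This gives PR-SD-PR-PR-PR, as the Appendix states. Visits 1 and 3 are about 20 weeks apart on the 10-week schedule, so the 4-week condition is met.

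**2. Apply footnote a.** On the measured sums (PR-SD-PR-SD-SD) no two adjacent visits reach 30%. On the carried-forward labels, adjacent PRs appear from visit 3, but only because the non-adjacent rule has already confirmed the PR. The rules differ for certain when nothing can be carried forward:

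| Sequence | Protocol 10.6.1.1 | Footnote a |
|---|---|---|
| PR-SD-PR-PD | PR | SD |
| PR-SD-PR, last scan | PR | SD |

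**3. Direction and unit of size.** Reading the footnote's 4-week interval as the protocol's, any two consecutive determinations that satisfy footnote a also satisfy 10.6.1.1; the reverse is not true. Responders under the consecutive rule are therefore a subset, and ORR can only fall or stay the same. One reclassified patient moves ORR by 1/N: 1/400 = 0.25 percentage points at the planned maximum, or 1/198 = 0.51 points at the enrolment reported for 30 June 2014.

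**4. CBR.** Footnote c of Table 8.1.1 counts PR of any duration and SD of 24 weeks or longer. A PR-SD-PR pattern needs three scans. The third is scheduled at Week 30 with a 2-week window, so at the earliest Week 30 − 2 = Week 28, which exceeds 24. The patient relabelled SD still counts.

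**5. The rest of footnote a.** Protocol 10.6.1.1 counts confirmed responses, so the branch for studies without confirmation never applies. The closing exclusion of PR from the PR rule must mean CR, as in 10.6.1.1.

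**6. Programmer note.** Scans are "repeated at Week 10, Week 20, Week 30, Week 40, and Week 50/EOT" (protocol 7.3), and in 4.1 they "will be performed for Screening, at Week 10, and 10 weekly thereafter". Up to Week 50 that makes 5 scans.
- *If the note means those two scans only:* it uses 2 of 5 scans. Possible confirming pairs are C(5,2) = 10, of which 1 (Weeks 20 and 50) is available, and 0 of the 4 adjacent pairs. SD at Weeks 10 and 20, PR at Weeks 30 and 40, then PD at Week 50 is a confirmed PR under the protocol, but the note's data show SD then PD.
- *If it means data up to Week 50:* the overall block repeats the Week 50 block, and scans from Week 60 on are dropped.

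Neither reading fits an overall-period block defined until progression.

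**7. Protocol 10.6.1.2 beside 10.6.1.1.** Two determinations of CR already make a best response of CR. Read literally, the 10.6.1.2 sentence leaves no route to a best response of PR, whereas 10.6.1.1 assigns PR on two determinations of PR or better.

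**The case against.** The strongest reply concerns the note. Either literal reading makes the overall block contradict footnote a or duplicate the Week 50 block, so the note was probably written for the two visit blocks and to say that the table is not a Kaplan-Meier analysis. That stands. A reader might infer that the SAP bases the whole response table on two scans; the documents do not settle this, and the counts in step 6 hold only under the strictest reading. The protocol shares the blame: 10.6.1.1 defines ORR by responses at time points it has not yet named.

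Other tempting inferences also fail:
- *The Appendix patient herself is lost.* Not for certain, because carried-forward labels give her adjacent PRs.
- *Table 8.2.1 gives a non-responder a response duration.* Its footnote sets a start date and does not clearly admit PR-SD-PR.
- *The table defines n in two incompatible ways.* Each block opens with a bare-count row, which can hold the non-missing count; the category rows hold category counts.
- *Stable patients with only non-measurable disease drop out of CBR.* Appendix 14.1.25 already treats Non-CR/Non-PD as SD in general.

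Finally, the SAP supplied consists of table shells and listings, and Appendix 14.1.28 allows decisions to sit in separate reporting and analysis plan documentation. A correct derivation may exist there. The footnotes would still state a different rule from the protocol.

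**Conclusion.** The point holds for three wording conflicts.

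1. The consecutive requirement in Tables 8.1.1 and 8.1.3 is stricter than protocol 10.6.1.1 and the Appendix example. It can only lower ORR and moves affected patients from PR to SD. CBR is unchanged for an intervening SD on scheduled scans. The footnote does not say whether an intervening unknown assessment breaks the run, and nothing here relies on that case.
2. The programmer note is unscoped. Its likely intent is harmless; its literal text conflicts with the overall-period block, footnote a and the first paragraph of 10.6.1.1.
3. Protocol 10.6.1.2 contradicts 10.6.1.1 on how a PR is confirmed.

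The number of affected patients cannot be derived from the documents. Six tables carry the Table 8.1.1 layout (8.1.1, 8.1.2 and S1 to S4.8.1.1). No hypothesis is tested, so no error rate or power is involved. The wording should be corrected before the tables are programmed, so that nobody has to choose between rules with the data in view.

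**What to change.** - **Footnote a, Table 8.1.1:** replace the CR and PR rules with those of protocol 10.6.1.1. This removes the consecutive requirement and the no-confirmation branch, and makes the PR rule exclude patients who qualify for CR. Use the same rule under Tables 8.1.3 and 8.2.1.
- **Programmer note:** limit the Week 20 and Week 50 sentence to those two blocks. Define each block as best response from all assessments up to that visit, since one visit alone cannot confirm a response.
- **Overall block:** derive it from all assessments up to progression, subject to the Appendix 14.1.16 limits on scans more than 30 days after the last dose and scans after new anticancer therapy.
- **Protocol 10.6.1.2:** reconcile its confirmation sentence with 10.6.1.1, so that ORR and CBR use one rule. The same change could say which time points 10.6.1.1 means.
- **Optional:** a cross-reference to Appendix 14.1.25 for non-measurable disease.

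Cost: three SAP footnotes, one programmer note and one reconciling protocol sentence. No new data.

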10.2 General statistical methods

The data will be summarized with respect to demographic and baseline characteristics, efficacy observations and measurements, and safety observations and measurements. Primary efficacy and safety/tolerability analysis will be conducted at 15 months of median follow up time, i.e. at approximately two times the median PFS reported in the BOLERO-2 study (Baselga et al. 2012; Yardley D. et al. 2014). Categorical variables will be summarized by absolute and relative frequencies. Continuous variables will be summarized by descriptive statistics (number of valid and missing observations, mean, standard deviation, median, minimum, and maximum).

Time to event data including rates of affected patients will be assessed using the Kaplan-Meier method. Two-sided 95% confidence intervals will be provided for the main statistical estimators.

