10.6 Secondary objectives

10.6.1 Efficacy endpoints

Efficacy endpoints will be analyzed on the Full Analysis Set (primary analysis) and on the Per Protocol Set (supportive analysis).

Efficacy endpoints based on radiological assessments of tumor burden will be derived using local radiologist's/ investigator's assessment. If a patient has not had an event before exiting the study, his or her data will be censored at the date of last adequate tumor assessment.

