14.1.22 Duration of response

The analysis of the following variables should be performed with much caution when restricted to responders since treatment bias could have been introduced. There have been reports where a treatment with a significantly higher response rate had a significantly shorter duration of response but where this probably primarily reflected selection bias which is explained as follows: It is postulated that there are two groups of patients: a good risk group and a poor risk group. Good risk patients tend to get into response readily (and relatively quickly) and tend to remain in response after they have a response. Poor risk patients tend to be difficult to achieve a response, may have a longer time to respond, and tend to relapse quickly when they do respond. Potent agents induce a response in both good risk and poor risk patients. Less potent agents induce a response mainly in good risk patients only. This is described in more detail by Morgan (1988)

It is recommended that an analysis of all patients (both responders and non-responders) be performed whether or not a “responders only” descriptive analysis is presented. An analysis of responders should only be performed to provide descriptive statistics and even then interpreted with caution by evaluating the results in the context of the observed response rate

If an inferential comparison between treatments is required this should only be performed on all patients (i.e. not restricting to “responders” only) using appropriate statistical methods such as the techniques described in Ellis et al (2008). It should also be stated in the protocol if duration of response is to be calculated in addition for unconfirmed response.

For summary statistics on “responders” only the following definitions are appropriate.

(Specific definitions for an all-patient analysis of these endpoints are not appropriate since the status of patients throughout the study is usually taken into account in the analysis).

Duration of overall response (CR or PR): For patients with a CR or PR (which may have to be confirmed the start date is the date of first documented response (CR or PR) and the end date and censoring is defined the same as that for time to progression.

[figure not shown]
The following two durations might be calculated in addition for a large Phase III study in which a reasonable number of responders is seen.

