Asian: Indonesia, India, Vietnam, Turkey, South Korea, Thailand, Malaysia, Taiwan or Jordan.

Non-Asian: Australia, Morocco, South Africa or Tunisia.

^a Time to overall response is the time from date of start of treatment to the date of event defined as overall response. Overall response rate: Patients with best overall response rate of CR or PR: CR: At least two consecutive determinations of CR or PR for at least 4 weeks or one determination of CR or PR where confirmation not required prior to PD.

^b Percentiles with 95% CIs are calculated from PROC LIFETEST output using method of Brookmeyer and Crowley (1982).

^c Event-free probability estimate is the estimated probability that a patient will remain event-free up to the specified time point. Event-free probability estimates are obtained from the Kaplan-Meier survival estimates.

Table 8.1.4 Time to Overall Response Overall and in Asian Subgroup – Per Protocol Set

This table will be created using the same layout as Table 8.1.3.

Table 8.1.5 Distribution of Time to Overall Response Overall and in Asian Subgroup by Analysis Set

This table will be created using the same layout as Table 7.3.3.

Table 8.2.1 Duration of Clinical Response Overall and in Asian Subgroup - Full Analysis Set

Overall Response	Statistic	Asian (N=xx)	Non-Asian (N=xx)	Total (N=xxx)
Duration of overall response (CR+PR) (weeks) ^a	n	xx	xx	xx
	Mean (SD)	xx (xx.x)	xx (xx.x)	xx (xx.x)
	Median	xx	xx	xx
	Min, Max	xx.x, xx.x	xx.x, xx.x	xx.x, xx.x
Proportion with overall response (CR+PR) > 24 weeks	n (%)	xx (xx)	xx (xx)	xx (xx)
	95%CI	(xx.x, xx.x)	(xx.x, xx.x)	(xx.x, xx.x)
Duration of clinical benefit (CR+PR+SD >= 24 weeks) (weeks) ^b	n	xx	xx	xx
	Mean (SD)	xx (xx.x)	xx (xx.x)	xx (xx.x)
	Median	xx	xx	xx
	Min, Max	xx.x, xx.x	xx.x, xx.x	xx.x, xx.x
Proportion with clinical benefit (CR+PR+SD >= 24 weeks) > 24 weeks	n (%)	xx (xx)	xx (xx)	xx (xx)
	95%CI	(xx.x, xx.x)	(xx.x, xx.x)	(xx.x, xx.x)
Duration of stable disease (weeks) ^c	n	xx	xx	xx
	Mean (SD)	xx (xx.x)	xx (xx.x)	xx (xx.x)
	Median	xx	xx	xx
	Min, Max	xx.x, xx.x	xx.x, xx.x	xx.x, xx.x
Proportion with stable disease > 24 weeks	n (%)	xx (xx)	xx (xx)	xx (xx)
	95%CI	(xx.x, xx.x)	(xx.x, xx.x)	(xx.x, xx.x)
For patients right-censored ^d				
Time elapsed from last tumor evaluation to end of study (weeks) ^e	n	xx	xx	xx
	Mean (SD)	xx (xx.x)	xx (xx.x)	xx (xx.x)
	Median	xx	xx	xx
	Min, Max	xx.x, xx.x	xx.x, xx.x	xx.x, xx.x

SD: Standard deviation. CI: Confidence interval.

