Asian: Indonesia, India, Vietnam, Turkey, South Korea, Thailand, Malaysia, Taiwan or Jordan.

Non-Asian: Australia, Morocco, South Africa or Tunisia.

^a Duration of overall response: Time from the date of the first of two documented CR or PR for at least 4 weeks or one documented CR or PR where confirmation not required to the date of first documented disease progression or death due to underlying cancer.

^b Duration of clinical benefit: Time from the date of the first of CR (any duration), PR (any duration) or SD (with duration of 24 weeks) to the date of first documented disease progression or death due to underlying cancer.

^c Duration of stable disease: Time from the start of treatment date to date of first documented disease progression or death due to underlying cancer.

^d For effectiveness evaluation (progression-free survival), patients without progression or death are right-censored at the date of their last tumor response evaluation.

^e Time from the date of last tumor assessment to date of end of study visit. In case of end of study visit date missing, date of last follow-up visit or date of end of treatment, whichever occurs later, will be used.

Table 8.2.2 Duration of Clinical Response Overall and in Asian Subgroup - Per Protocol Set

This table will be created using the same layout as Table 8.2.1.

Table 8.3.1 Progression-Free Survival Overall and in Asian Subgroup - Full Analysis Set

	Asian (N=xx)		Non-Asian (N=xx)		Total (N=xxx)	
	No. of patients at risk	Event-free probability estimates (%) ^c	No. of patients at risk	Event-free probability estimates (%) ^c	No. of patients at risk	Event-free probability estimates (%) ^c
Progression-free survival (PFS) time ^a						
Week 4	xxx	x.x	xxx	x.x	xxx	x.x
Week 10	xxx	x.x	xxx	x.x	xxx	x.x
Week 20	xxx	x.x	xxx	x.x	xxx	x.x
Week 30	xxx	x.x	xxx	x.x	xxx	x.x
Week 40	xxx	x.x	xxx	x.x	xxx	x.x
Week 50	xxx	x.x	xxx	x.x	xxx	x.x
Etc. (as appropriate)						
Total number of events, n (%)	xx (xx.x)		xx (xx.x)		xx (xx.x)	
Progression, n (%)	xx (xx.x)		xx (xx.x)		xx (xx.x)	
Death, n (%)	xx (xx.x)		xx (xx.x)		xx (xx.x)	
Total number of censored, n (%)	xx (xx.x)		xx (xx.x)		xx (xx.x)	
Percentiles (95%CI) (weeks) ^b						
25 th percentile	xx.x (xx.x, xx.x)		xx.x (xx.x, xx.x)		xx.x (xx.x, xx.x)	
Median	xx.x (xx.x, xx.x)		xx.x (xx.x, xx.x)		xx.x (xx.x, xx.x)	
75 th percentile	xx.x (xx.x, xx.x)		xx.x (xx.x, xx.x)		xx.x (xx.x, xx.x)	

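### SAP Table 8.2.1 and its copies summarise right-censored durations with raw means, medians and ranges where the protocol calls for Kaplan-Meier

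*SAP*

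**What the plan says.** **SAP.** Table 8.2.1 has three duration rows: overall response, clinical benefit and stable disease. The first is labelled "Duration of overall response (CR+PR) (weeks"). Each gets n, mean (SD), median, minimum and maximum. Each is followed by a crude frequency, for example "Proportion with overall response (CR+PR) > 24 weeks", with a 95% CI. There is no count of events, no count of censored patients and no CI for a median.

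Footnotes a to c give each duration an end date only at progression or cancer death; footnote c reads "Duration of stable disease: Time from the start of treatment date to date of first documented disease progression or death due to underlying cancer". Footnote d says that "patients without progression or death are right-censored at the date of their last tumor response evaluation", but it is worded for PFS. The block for right-censored patients reports only the gap from last scan to end of study. Table 8.2.2 and Tables S1 to S4.8.2.1 reuse the layout.

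**Protocol.** Section 10.2: "Time to event data including rates of affected patients will be assessed using the Kaplan-Meier method". Section 10.6.1, for a patient without an event: "his or her data will be censored at the date of last adequate tumor assessment". Appendix 14.1.22, for duration of response: "the end date and censoring is defined the same as that for time to progression". The same appendix section gives duration of stable disease the same rule. Row G of Table 14-5 also censors deaths from other causes for duration of response, and 14.1.38 lists censoring reasons that extend to it.

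**The concern.** The protocol treats these durations as censored variables, but the shell treats them as fully observed. A patient who has neither progressed nor died of cancer has no end date under footnotes a to c. The programmer must either leave her out or enter her censoring time as a finished duration. The first keeps mainly the short durations; the second cuts off the long ones.

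The results will be read beside the Kaplan-Meier PFS in Table 8.3.1, and readers will take the two as comparable. The choice looks like an oversight, because the SAP uses Kaplan-Meier for AE resolution (6.14), ECOG deterioration (7.3.1), PFS (8.3.1) and time to response. The footnote of that last table, 8.1.3, reads "Event-free probability estimates are obtained from the Kaplan-Meier survival estimates".

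**Working it through.** The plan gives no duration figure to reproduce, so the check has two parts: the text, and an illustration of size on stated assumptions.

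**Text.** Section 10.2 supplies the estimator. Section 10.6.1, Appendix 14.1.22, row G of Table 14-5 and 14.1.38 supply the censoring. Duration of clinical benefit is defined only in the SAP; it has the same end date, so sections 10.2 and 10.6.1 govern it. A mean with SD, a range and a crude n (%) cannot carry a censoring rule.

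**Duration of response: inputs.** All are assumptions except the visit schedule.
- True duration T is exponential with median m = 8, 12 or 20 months. True mean = m/ln 2 = 11.5, 17.3, 28.9. The true share beyond 24 weeks (5.52 months) = 2^(-5.52/m) = 62%, 73%, 83%.
- First response is at the first scheduled scan, week 10 (2.3 months), so censoring time C = follow-up minus 2.3 months. Patients with C ≤ 0 are dropped.
- Follow-up is centred on 15 months, the median planned in protocol 10.2: uniform 3–27 or uniform 9–21. Two further patterns take uniform 9–21 but let 10% or 25% of patients leave at 2 to 6 months.

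The 2-to-6-month window is what a patient enrolled between 1 July and 31 October 2014 would have had if she left on 31 December 2014. SAP Table 1.1 counts enrolment from 1 July 2014, protocol 4.1 closes it by 31 October, and SAP Tables 1.3 and 1.4.1 list completion of the access programme on 31 December 2014 as an exit reason.

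**Formulas, censored time counted.** Raw share beyond 24 weeks = P(T > 5.52) × P(C > 5.52). The raw median solves P(T > t) × P(C > t) = 0.5.

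Example, m = 12, follow-up 3–27, so C is uniform on 0.7–24.7:
- share = 0.727 × (24.7 − 5.52)/24 = 0.727 × 0.799 = 0.58;
- median: at t = 6.9, 2^(-6.9/12) × (24.7 − 6.9)/24 = 0.671 × 0.742 = 0.50.

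| Follow-up (months) | Raw median, censored time counted | Raw share > 24 weeks |
|---|---|---|
| True value | 8 / 12 / 20 | 62 / 73 / 83% |
| Uniform 3–27 | 5.5 / 6.9 / 8.6 | 50 / 58 / 66% |
| Uniform 9–21 | 7.4 / 8.8 / 10.2 | 62 / 73 / 83% |
| 9–21, 10% leave at 2–6 | 6.8 / 8.1 / 9.5 | 56 / 66 / 75% |
| 9–21, 25% leave at 2–6 | 4.9 / 7.0 / 8.3 | 47 / 56 / 63% |

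Under uniform 9–21 the share is exact because the shortest C is 9 − 2.3 = 6.7 months, beyond 24 weeks.

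The raw mean is 7.0/8.3/9.7 under uniform 3–27 and 7.5/8.8/10.1 under uniform 9–21. With censored patients left out, the medians are 4.5/5.2/5.9 and 4.6/5.1/5.6. Simulated Kaplan-Meier estimates gave 62/73/83% at 24 weeks in every pattern, and the true median to within 0.1 month wherever follow-up reached it.

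**Stable disease, from treatment start.** With assumed true medians of 6/8/12 months, the raw median with censored time counted is 5.2/6.3/8.0 (uniform 3–27) and 6.0/8.0/10.2 (uniform 9–21). With completed durations only it is 4.2/4.8/5.7 and 4.5/5.1/5.8.

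**A case tied to a figure in the protocol.** The final BOLERO-2 median PFS of 7.82 months is 34.0 weeks. Used as an assumed true median:
- follow-up uniform 5–25 months: raw median 29.5 weeks counted, 21.1 completed only;
- follow-up uniform 10–20 months: 34.0 counted, 22.1 completed only;
- uniform 5–25 plus switching to commercial drug (assumed median 24 months): 24.5 and 18.5.

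Kaplan-Meier returns 34.0 to 34.1 weeks. The raw mean with censored time counted is 29.1 to 35.6 weeks against a true 49.1.

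**The case against.** - **Appendix 14.1.22 never names Kaplan-Meier, and allows responder-only descriptive statistics.** True; the estimator comes from 10.2. But the appendix defines censoring for those same responder-only durations, and a Kaplan-Meier median is also descriptive.
- **A median cell could hold a Kaplan-Meier median, and the supplied SAP is mainly shells, so a rule may exist elsewhere.** Both are possible. The mean (SD), range and crude n (%) would still be raw, and the layout lacks the event counts, censored counts and CIs of Tables 7.3.1, 8.1.3 and 8.3.1.
- **The 31 December 2014 exit is the old end of study.** Protocol 4.1 and 4.2 now continue until local reimbursement or commercialisation, or until all patients have stopped treatment. The SAP still lists that exit, perhaps as a legacy category, alongside switching to commercial drug. Early censoring is plausible, but the number of patients is not given.
- **Protocol 10.6.1.1 requires confirmation at least 4 weeks later, and scans are 10-weekly.** This shrinks the gaps. Require both T and C to exceed 2.3 months. The true share is then 2^(-(5.52 − 2.3)/m) = 76/83/89%. P(C > 5.52) becomes 0.90/(0.90 + 0.10 × 1.4/4) = 0.963 with 10% early exits, 0.75/(0.75 + 0.25 × 1.4/4) = 0.896 with 25%, and 19.18/22.4 = 0.856 under uniform 3–27. The shortfalls are about 3, 8–9 and 11–13 points. The median stays low: for m = 12 under uniform 3–27, 2^(-6.3/12) × (1 − 6.3/22.4) = 0.50, so the raw median is 6.3 + 2.3 = 8.6 months against 12 + 2.3 = 14.3. Footnote a also admits unconfirmed responses where confirmation is not required.
- **Appendix 14.1.22 defines stable-disease duration over CR, PR and SD together.** The SAP row does not say whether it covers SD alone. The censoring point applies either way.
- **The tables are supportive and the study tests no hypothesis.** True, and this limits the weight of the point.

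**Conclusion.** The concern holds. As laid out, Table 8.2.1 and its copies depart from protocol 10.2 and cannot apply the protocol's censoring rule.

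The raw mean is low whichever way censored patients are handled. The raw median and the share beyond 24 weeks are low if censored patients are dropped or if censoring comes early. With late censoring and censored time counted, the share is unbiased and shorter medians are recovered.

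The sizes rest on assumed exponential durations, assumed follow-up patterns and censoring unrelated to progression, so they form a range and not a forecast. The departure from the protocol does not depend on them. ORR, CBR, PFS and the primary safety analysis are unaffected. It should be fixed before the tables are programmed.

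**What to change.** In Tables 8.2.1, 8.2.2 and S1 to S4.8.2.1:

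1. In the three duration rows, replace mean (SD), median and range with number of events, number censored, and Kaplan-Meier quartiles with 95% CIs.
2. Add the time-to-progression censoring rule to footnotes a to c: censor at the last adequate tumour assessment, and censor deaths from causes other than the cancer.
3. For response (among responders, from first response) and stable disease (from treatment start), replace the crude share beyond 24 weeks with the Kaplan-Meier probability at 24 weeks.
4. Keep the clinical-benefit row beyond 24 weeks as a frequency with a Clopper-Pearson CI, as protocol 10.6.1.2 does for the CBR. Patients with stable disease enter it only after 24 weeks, so a Kaplan-Meier value there would be largely fixed by construction.

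The cost is a shell edit and modest programming, because the event and, for response, the start date differ from PFS. No new data are needed. Some intervals will be wide and some medians not reached; for example, a true median of 20 months cannot be reached with at most 21 − 2.3 = 18.7 months of follow-up after response.
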